191 clinical events) within 30 days. The results showed that anticoagulation with
192 bivalirudin alone, as compared with heparin plus glycoprotein IIb/IIIa inhibitors,
193 resulted in a reduced 30-day rate of net adverse clinical events (9.2% vs. 12.1%;
194 relative risk, 0.76; 95% confidence interval [CI] 0.63 to 0.92; P=0.005), owing to a
195 lower rate of major bleeding (4.9% vs. 8.3%; relative risk, 0.60; 95% CI, 0.46 to
196 0.77; P<0.001). Treatment with bivalirudin alone, as compared with heparin plus
197 glycoprotein IIb/IIIa inhibitors, resulted in significantly lower 30-day rates of death
198 from cardiac causes (1.8% vs. 2.9%; relative risk, 0.62; 95% CI, 0.40 to 0.95;
199 P=0.03) and death from all causes (2.1% vs. 3.1%; relative risk, 0.66; 95% CI, 0.44

200 to 1.00; P=0.047). One-year outcomes in the HORIZONS-AMI trial continued to
201 show that bivalirudin is associated with a lower rate of major bleeding (15.6% versus
202 18.3%, p=0.0001) and mortality (3.5% versus 4.8%, p=0.037). In HORIZONS-AMI,
203 there was an increased risk of acute stent thrombosis within 24 hours in the
204 bivalirudin group, which might due to delayed onset of pharmacodynamic effects of
205 clopidogrel.

206

207 **5. Study design, randomization and blinding**

208 **5.1 Study design**

209 This study is a prospective, multicenter, randomized, active controlled,
210 open-label, superiority trial.

211 **5.2 Study procedure**

212 Patients meet ALL the inclusion criteria and NONE of the exclusion criteria
213 will be randomly assigned to 3 arms after informed consent is signed. Study
214 medications will be given in the cath lab before angiography. Activated clotting time
215 (ACT) will be measured 5 min after heparin or bivalirudin administration. Repeat
216 bivalirudin or heparin bolus will be given if ACT is less than standard level
217 according to protocol. Bailout tirofiban can be used in patients allocated in the
218 bivalirudin arm or heparin arm if there is significant thrombus in the culprit vessel.
219 Patients will be visited at 30 days, 6 months and 12 months via telephone or clinic.
220 Detailed study procedures are listed in table 1.

221 **5.3 Randomization**

222 Patients meeting ALL the inclusion criteria and NONE of the exclusion criteria
223 will be enrolled. Randomization will be performed in catheterization laboratory
224 immediately after informed consent is signed, using computer-generated block

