225 randomization sequence sealed in an envelope.

226 **5.4 Blinding**

227 Study medications are known by both investigators and subjects. However,
228 independent clinical events committee is blinded to the treatment allocation.

229

230

231

232 Table 1: Study procedure table

| | Baseline | Visit 1 30 days | Visit 2 6 months | Visit 3 12 months |
|--------------------------------------|----------|--------------------|---------------------|----------------------|
| window | | ±7d | ±14d | ±30d |
| Informed consent | X | | | |
| Inclusion/exclusion criteria | X | | | |
| Randomization | X | | | |
| Medical history/demographic features | X | | | |
| Vital signs | X | | | |
| Routine blood and urine test | X | | | |
| Biochemical test | X | | | |
| CK/CKMB and troponin T | X | | | |
| Activated clotting time | X | | | |
| 12- leader electrocardiogram | X | | | |
| Important clinical symptoms | X | X | X | X |
| Clinical evaluation | X | X | X | X |
| Adjunctive medications | X | X | X | X |
| Coronary angiography | X | | | |
| Adverse cardiac events recording | | X | X | X |
| Adverse events recording | | X | X | X |

233 **6. Study population:**

234 **6.1 Target population:**

235 2100 patients who meet the inclusion criteria and receive study medications
236 before coronary angiography.

237 **6.2 Inclusion criteria**

238 (1) Patients aged from 18~80 years, male or female;

239 (2) AMI (STEMI or NSTEMI) patients with planned emergency PCI.

240 ● STEMI within 12 hours after symptom onset or within 12~24 hours with ongoing
241 chest pain, continuous ST segment elevation or new left bundle block.

242 ● NSTEMI within 72 hours after symptom onset.

243 (3) Staged revascularization for non-culprit vessel should be performed after 30 days.

244 (4) Antiplatelet agents (aspirin and clopidogrel, both loading and maintenance dose)
245 are given before PCI per guidelines.

246 (5) Subjects or legal representatives voluntarily participated and signed informed
247 consent, willing to accept study medications and clinical follow-ups.

248 **6.3 Exclusion criteria:**

249 (1) Patients not suitable for PCI; thrombolytic therapy administered before
250 randomization; cardiogenic shock;

251 (2) Any anticoagulant (heparin/LMWH, fondaparinux, warfarin or bivalirudin) or
252 tirofiban administered within 48 hours before randomization;

253 (3) Active or recent major bleeding or bleeding predisposition, including retinal or

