254 vitreous hemorrhage within one month, GI or urinary track hemorrhage within 3
255 months, intracranial hemorrhage within 6 months or cerebral infarction within 3
256 months;

257 (4) Patients at high risk of secondary bleeding, including active gastric ulcer,
258 ulcerative colitis, intracranial aneurysm, etc.;

259 (5) Major surgery (including ophthalmologic operation or neurosurgery) within 1
260 month;

261 (6) Clinical syndrome suspicious for aortic dissection, pericarditis or endocarditis;

262 (7) Uncontrolled blood pressure (>180/110 mmHg);

263 (8) Known hemoglobin <10 g/dL or platelet count <100 × 10⁹/L;

-
- 264 (9) Aminotransferase level >3x the upper limit of normal;
265 10) Severe renal insufficiency (eGFR<30 mL/min/1.73m²);
266 (11) History of heparin induced thrombocytopenia;
267 (12) Known allergy to study medications or device (heparin, bivalirudin, tirofiban,
268 aspirin, clopidogrel, stainless steel, contrast medium or hirudin) or allergic
269 constitution;
270 (13) Patient pregnant or lactating, or planned pregnant within 1 year;
271 (14) Study subjects with poor compliance judged by investigators or patient ever
272 participated in another clinical trial and has not completed the follow-up to the
273 primary endpoint.

274

275 **6.4 Criteria of patient removal, treatment discontinuation and drop out**

276 **6.4.1 Criteria of removal**

277 Patient should be removed if:

- 278 • Misdiagnosis.
- 279 • Without any record of physical or laboratory test results.
- 280 • Do not meet the inclusion criteria or meet at least one exclusion criteria.

281 The reason of removal should be written down and the case report form (CRF) should
282 be preserved for audit check. Removal patients will not be included in the efficacy
283 analysis but could be included in the safety analysis if there are any records regarding
284 efficacy or safety.

285 **6.4.2 Criteria of treatment discontinuation**

286 Discontinuation of any study medication is defined as stopping experimental
287 treatment. The reason of discontinuation should be clearly noted in the original
288 medical records and CRF.

289 Treatment should be discontinued if:

- 290 • Patient withdrawal of informed consent.
- 291 • Intolerable side effects of study medications

-
- 292 • Severe allergy that cannot be relieved by anti-allergic therapy
 - 293 • Adverse events or abnormal laboratory test results indicating that
 - 294 continuation of treatment would be inappropriate.

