465 medical records.

466 • To ensure all errors and missing data are corrected or illustrated and signed
467 by the investigator.

468 • To ensure each therapeutic change, concomitant medication and complication
469 is recorded accurately.

470 • To ensure that all patient withdrawals or loss of follow-up are recorded in the
471 CRF.

472 • To ensure that all AEs are recorded and all SAEs are reported per standard
473 procedure.

474 • To ensure that the delivery, storage and recycling of study drugs abide to
475 regulatory requirements and are recorded.

476

477 **12. Statistical analysis**

478 BRIGHT is a prospective, multicenter, randomized, open label, active controlled
479 trial. AMI patients with planned emergency PCI will be enrolled and randomly
480 assigned to be treated with bivalirudin, heparin alone or heparin plus tirofiban.

481 Analysis for primary endpoint will be performed at the time that 30 day follow-up for
482 all subjects are completed. Analysis for secondary endpoints will be performed when
483 12-month follow-up are completed.

484 **12.1 Sample size calculation**

485 The primary endpoint is 30-day NACE, a composite of all-cause death,
486 reinfarction, ischemia driven TVR, stroke or any bleeding. Incidence of primary
487 endpoint will be compared between bivalirudin group and two control groups
488 sequentially. Only when both p values of two step tests (bivalirudin versus heparin
489 alone and bivalirudin versus heparin plus tirofiban) are less than 0.05, then the

490 conclusions of bivalirudin being superior to controls will be accepted.

491 The study hypothesis is that bivalirudin is superior to both heparin alone and
492 heparin plus tirofiban on 30-day NACE.

493 $H_0: P_B = P_C$

494 $H_1: P_B \neq P_C, \alpha = 0.05$ (two-sided)

495 P_B denotes NACE rate in the bivalirudin group, P_C NACE rate in the control group.

496 Assuming a 30-day NACE rate of 11.5% in the heparin alone group and 12.1%
497 in the heparin plus tirofiban group, allowing for 5% lost to follow-up, with a
498 two-sided alpha of 0.05, 700 patients per group would provide >90% power to
499 demonstrate a 45% reduction with bivalirudin for each comparison. Enrollment of
500 2,100 total patients (~700 per group) was therefore planned.

501

502 **12.2 Analysis populations**

503 All primary and major secondary endpoints will be analyzed both on an
504 intent-to-treat basis (all patients analyzed as part of their assigned treatment group)

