505 and on a per protocol basis (patients analyzed as part of their assigned treatment group
506 only if they actually received their assigned treatment). The primary statistical
507 analyses will be by intent-to-treat.

508 • **Intention-to-treat (ITT) set:** Patients who meet the study inclusion criteria, sign
509 the written informed consent and receive study medications after randomization
510 and have any assessment for the primary endpoint will be included in the ITT set.
511 ITT set will be used as baseline characteristics and endpoint analysis.

512 • **Per protocol (PP) set:** Patients with a successful procedure and complete
513 follow-up information will be included in the PP set.

514

515 **12.3 Statistical method**

516 Data will be analyzed using SPSS V19.0 software package. Two sided test with
517 alpha level of 0.05 will be used.

518 Baseline demographic and clinical variables will be summarized for each of the
519 treatment groups for the ITT set. All continuous variables will be summarized using
520 means, standard deviations, medians, interquartile ranges, minimums and maximum

521 values and two-sided 95% confidence intervals. Categorical variables will be
522 summarized using frequencies and percentages with two-sided exact 95% confidence
523 intervals. P-values comparing the two treatment groups will be presented for
524 descriptive purposes. Continuous data will be summarized using mean and standard
525 deviation and compared using Student's t-test or one-way ANOVA. Time-to-event data
526 were compared with the log-rank test.

527 Pre-specified subgroups for analysis include gender, age, type of AMI, heart
528 failure, diabetes, anemia, renal insufficiency, arterial access, multivessel disease,
529 history of cardiovascular events, high bleeding risk, and PCI for left anterior
530 descending coronary artery.

531

532 **13. Quality Control**

533 Sponsor shall appoint monitors to conduct systematic monitoring for the study in
534 accordance with GCP principles to ensure the study is carried out according to the
535 protocol and the case report form is identical with original data. The monitors should
536 also assess compliance corresponding to the regulations and protocol.

537 Investigators must ensure the integrity of the medical files. All study files will be
538 reviewed by the sponsor and monitors. Monitors should ensure the following: the

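### Inclusion criterion (3) concerns a procedure after randomisation; read literally with the removal rule and the ITT definition, it lets patients be dropped from the primary analysis for what happens during the 30-day endpoint window

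*Protocol*

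**What the plan says.** Four parts of the protocol bear on this.

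- **Criterion.** Section 6.2, item (3), repeated in the synopsis: "Staged revascularization for non-culprit vessel should be performed after 30 days".
- **Timing.** Section 5.3 places randomisation in the catheterization laboratory, "immediately after informed consent is signed, using computer-generated block" randomisation. Section 5.2 adds that study "medications will be given in the cath lab before angiography".
- **Removal.** Section 6.4.1 lists among the grounds for removal: "Do not meet the inclusion criteria or meet at least one exclusion criteria". It continues: "Removal patients will not be included in the efficacy" analysis, although they may enter the safety analysis.
- **Analysis set.** The ITT set in 12.2 begins: "Patients who meet the study inclusion criteria, sign", and goes on to require consent, receipt of study medication and some primary-endpoint assessment. The opening of 12.2, like the synopsis, instead describes an "intent-to-treat basis (all patients analyzed as part of their assigned treatment group"), and makes ITT the primary analysis.

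**The concern.** An eligibility criterion should describe the patient at entry. This one describes when a later procedure takes place. Non-culprit disease is not seen until the angiogram, which follows randomisation and the first dose, so whether the criterion is satisfied depends on care over the next 30 days. Section 6.4.1 does not limit removal to failures known at baseline, and the ITT definition repeats the eligibility condition.

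The 30 days during which a patient could fail criterion (3) are the same 30 days over which NACE is counted. NACE includes reinfarction and any bleeding. A second procedure in that window could follow recurrent symptoms or cause a bleed that counts. Investigators know the allocation (5.4). The blinded events committee classifies events; the protocol does not give it the decision on who is removed. Exclusion could therefore be related to both arm and outcome, which is what analysis by intention to treat is meant to prevent.

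**Working it through.** **1. The plan's own figure.** Inputs from 12.1: control rates 11.5% (heparin) and 12.1% (heparin plus tirofiban), 45% relative reduction, two-sided alpha 0.05, 700 per group, 5% lost to follow-up. Bivalirudin rates are 0.55 × 11.5% = 6.325% and 0.55 × 12.1% = 6.655%. Evaluable patients per arm: 700 × 0.95 = 665. Power with a pooled-variance normal approximation is

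Φ{[d − 1.96·√(2p̄(1−p̄)/n)] / √([p_C(1−p_C)+p_B(1−p_B)]/n)}.

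For heparin, d = 0.05175 and p̄ = 0.089125, which gives (0.05175 − 0.03063)/0.01556 = 1.36 and power 91.3%. For heparin plus tirofiban it is 92.7%. The stated power above 90% is reproduced. The sample size is not in error, but it contains no separate allowance for removed patients.

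**2. Loss of numbers alone.** Suppose a share of each arm is removed and event rates do not change. The shares are assumptions.

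| Removed per arm | Power vs heparin | Power vs heparin plus tirofiban |
|---|---|---|
| 0% | 91.3% | 92.7% |
| 5% | 89.9% | 91.4% |
| 10% | 88.2% | 89.9% |

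This loss is modest. Bias is the main issue.

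**3. Bias when there is no true effect.** Let p be the true rate in both arms, f the share removed and r the event rate among those removed. The rate in the patients who remain is (p − f·r)/(1 − f). The protocol gives neither f nor r; both are assumed. With p = 11.5% and r = 30%:

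- *5% removed from bivalirudin, 3% from control.* Bivalirudin (0.115 − 0.015)/0.95 = 10.5%; control (0.115 − 0.009)/0.97 = 10.9%; RR 0.96. The standard error is about 0.0173, so the standardised shift is about −0.23. Two-sided rejection is 5.6%, of which 4.2% favours bivalirudin (nominal 2.5%).
- *10% and 5%.* Bivalirudin (0.115 − 0.030)/0.90 = 9.4%; control (0.115 − 0.015)/0.95 = 10.5%; RR 0.90. Rejection is 9.7%, of which 9.2% favours bivalirudin.
- *Equal shares, equal event rates.* The remaining rates are identical: RR 1.00, rejection 5.0%.

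With p = 12.1% the first two cases give RR 0.97 with 5.6% rejection and RR 0.91 with 9.2%. If more patients are removed from control, the direction reverses. These are rates for one comparison. Section 12.1 claims superiority only if both comparisons are significant, so they are not the error rate of the whole trial.

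**The case against.** The best counter-reading is that criterion (3) is a plan agreed at entry: any staged non-culprit procedure is to wait. Table 1 checks eligibility at baseline only. Sections 5.2 and 5.3 randomise patients who already meet all criteria. Nothing says eligibility is judged again at day 30. Departures from protocol are dealt with separately: 6.4.2 lists a major deviation as a reason to discontinue treatment, 16.1 requires the reason for a deviation to be recorded, and 6.4.3 retains all enrolled patients in follow-up. The opening of 12.2 would also keep everyone.

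Much of this stands. Removal is one reading of the text, not a certainty. But criterion (2) says the emergency PCI is planned, while criterion (3) has no such word. Section 6.4.3 governs follow-up, not membership of the efficacy set. The general ITT sentence contradicts the set definition beneath it and does not override it.

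The link to outcome is also open to challenge. Staged procedures are ordinarily planned, so an unplanned, symptom-driven one may fall outside the criterion. Revascularisation of a non-culprit vessel is not itself a NACE component, since the composite counts the target vessel. The link through reinfarction and procedural bleeding is plausible, but no figure in the protocol supports it.

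Finally, the point is a special case of an ITT definition that is conditional on eligibility. It still deserves mention, because here a patient could fail eligibility through something that happens after randomisation.

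**Conclusion.** The point holds as an internal contradiction that permits exclusion after randomisation for reasons that may be related to outcome. The protocol should not leave this open, and correcting it is cheap. The size and direction of any bias are unknown; the RRs of 0.96 and 0.90 rest on assumed removal shares and an assumed 30% event rate.

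Three stronger conclusions that a reader might draw are not supported.

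- *That the rules necessarily drop every such patient.* The baseline reading and the general ITT sentence point the other way.
- *That the damage is large.* Removing 5% of the heparin arm only, with a 50% event rate, gives (0.115 − 0.025)/0.95 = 9.5% and power of about 56%. Doing the same in the bivalirudin arm only, with no true effect, gives 9.5%/11.5%, a spurious reduction of about 18%. Both put every removal in one arm at extreme inputs. At the planned bivalirudin rate, the removed 5% would hold 2.5 of 6.325 percentage points, about 40% of that arm's events.
- *That equal removal inflates a true 45% reduction.* With the same 5% and 50% in both arms, the ratio is (6.325 − 2.5)/(11.5 − 2.5) = 0.425, an apparent 57.5% reduction. But that assumes bivalirudin does nothing in the removed patients. If they have the same 45% reduction, the ratio is 0.55(p − f·r)/(p − f·r) = 0.55, unchanged.

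**What to change.** - In 12.2, define the primary ITT set as all randomised patients analysed as assigned, and amend 6.4.1 so that removal does not take a randomised patient out of that set.
- In 6.2 and the synopsis, either move criterion (3) out of the eligibility list and restate it as a conduct instruction, or word it explicitly as an intention held at baseline.
- State that a departure is recorded as a protocol deviation, with the patient kept in the ITT set and all events counted.

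This takes no view on when staged revascularisation should be performed. The cost is protocol wording only. The sample size does not change: on the protocol's assumptions, power stays at 91.3% and 92.7% with 665 evaluable patients per arm.

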377 ● NACE at 12 months;

378 ● MACCE at 30 days and 12 months;

379 ● Any bleeding events (evaluated by BARC classification) at 30 days and 12
380 months.

381 **8.3 Safety endpoints**

382 ● Stent thrombosis (definite or probable by ARC definition) at 30 days and 12
383 months;

[figure not shown]
- Thrombocytopenia at 30 days;
- Any other abnormal symptoms, signs or laboratory test results with clinical significant.

387

388

389 **9. Study flowchart:**

390 See Figure 1.

391

392

393

394

395

396

Figure 1. Study flowchart

397 **10. AE/SAE reporting**

398

399 There are two classifications of adverse events: adverse event (AE), and serious adverse
400 event (SAE). Adverse events must be monitored until resolved or adequately explained. All
401 serious and unanticipated adverse events must be reported, regardless of the cause. They
402 should be reported to the local IRB/EC and Sponsor within 24 hours of knowledge of the
403 event.

404 **10.1 Definition of AE / SAE**

405 ● **AE**

406 Any adverse medical events occurring in a clinical trial, not necessarily
407 having a causal relationship with the study treatments. Adverse events could be
408 any signs (including abnormal laboratory values), symptom, or temporary disease,
409 whether related or unrelated to the study drug use. An adverse event may be
410 categorized as the following:

- 411 • Mild – signs or symptoms that do not interfere with the patients’ usual
412 activities or is transient and resolves without treatment of sequelae.
- 413 • Moderate – interferes with the patients’ usual activities and/or requires
414 symptomatic treatment.
- 415 • Severe – symptoms causing severe discomfort and significant impact the
416 patient’s usual activities and requires treatment.

417 ● **SAE**

418 A study-related event that is fatal, life-threatening, requires inpatient
419 hospitalization or prolongation of an existing hospitalization, requires
420 intervention to prevent permanent impairment/damage, or results in persistent or
421 significant disability.

422

423 **10.2 Observation and recording of AEs**

424 Investigators should collect and record all AEs occurring from the time of signing
425 informed consent for each subject to end of the follow-up in the clinical study.

426 For AEs, only medical events with clinical worsening compared to baseline are
427 recorded. Abnormal evaluation results at screening or baseline examination are not

428 considered AEs.

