429 For any AEs required to be recorded and described in the raw data, investigators
430 must determine their type, date, measures taken, outcomes, as well as their relevance
431 to study medications.

432 Subjects with AEs should receive clinical follow-up until the adverse event has
433 subsided (to a normal state or to baseline condition), or the patients achieves a stable
434 condition, or investigators believe the patients has reached a reasonable condition. If
435 the AEs did not subside to the above conditions, the investigators should continue to
436 provide the necessary treatment, and report and record the patient's progress. For
437 special circumstances, AEs should be treated in accordance with the instructions of
438 relevant administrative departments.

439

440 **10.3 Procedure of SAE reporting**

441 The Investigator must complete the SAE form for each SAE, whether related or
442 not to study drug. The event should be reported to the Investigational Review Board
443 (IRB)/ Ethics Committee (EC), national regulatory authority, sponsor and CRO within
444 24 hours (from the point in time when the SAE is identified by the site). The
445 information provided must be sufficient to allow for independent medical assessment
446 of the event. The Investigator should provide any additional follow-up information
447 regarding the event to the sponsor as soon as it becomes available.

448

449 **11. Data collection**

450 **11.1 Filling in case report form (CRF)**

- 451 • Principal investigator shall authorize personnel to fill in CRF.
- 452 • Investigators shall fill in the CRF in accordance to GCP principles and CRF
453 instructions to ensure that true, accurate and complete examination results are
454 transcribed into the CRF in a timely and standardized manner.
- 455 • Data recorded in the CRF should be verified with source medical recordings.
- 456 • Any change in the CRF should be marked with a deletion line. The correction
457 should be written down beside with the investigator's signature and date.
- 458 • Any abnormal data (great deviation from normal or clinically unacceptable)

459 should be verified and illustrated by the investigator.

460 • CRF data will be maintained by the sponsor and clinical research institutions.

461 **11.2 CRF auditing**

462 Monitors should audit patient consents and enrolment periodically in each
463 participating center:

464 • To ensure that data in the CRF are correct and are consistent with the original

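### Section 10.1 makes relatedness part of the SAE definition, which contradicts the rules in sections 10 and 10.3 to report serious events whatever their cause

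*Protocol*

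**What the plan says.** Four places in the protocol bear on which events count as serious and how they are reported.

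- **Section 10.1, SAE definition:** "A study-related event that is fatal, life-threatening, requires inpatient" hospitalisation or its prolongation, needs intervention to prevent permanent damage, or leads to lasting disability. The qualifier at the start applies to the whole list.
- **Section 10.1, AE definition, just above it:** an adverse event counts "whether related or unrelated to the study drug use". There is no causal condition.
- **Section 10, opening paragraph:** all "serious and unanticipated adverse events must be reported, regardless of the cause". These reports go to the local ethics committee and the sponsor within 24 hours.
- **Section 10.3:** "The Investigator must complete the SAE form for each SAE, whether related or" not to study drug. The event then goes within 24 hours to the ethics committee, the national regulator, the sponsor and the CRO.

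Section 10.2 treats causality as a separate item: for each recorded AE, investigators "must determine their type, date, measures taken, outcomes, as well as their relevance" to study medications.

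**The concern.** Seriousness and causality are different questions. An SAE definition normally asks only about outcome or severity, and relatedness is recorded afterwards. Section 10.1 merges the two, so the relatedness call comes before the SAE rules rather than after them. Section 10.3 then instructs sites to report SAEs whether or not they are related to study drug, but that instruction reaches only events already admitted by 10.1.

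What is at stake is whether a serious event judged unrelated is labelled an SAE, appears in the SAE tables and reaches the regulator and CRO within 24 hours. With approximately 82 centers planned, different sites may also resolve the conflict differently, so the SAE listing would not mean the same thing everywhere.

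**Working it through.** The plan gives no figure to reproduce and no arithmetic applies. The check is to follow one event through each rule.

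Take a patient readmitted during follow-up for an illness that the site considers to have nothing to do with the study.

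1. **Is it an AE (10.1)?** Yes. The AE definition covers unrelated events, and 10.2 requires all AEs from consent to the end of follow-up to be recorded.
2. **Is it an SAE (10.1)?** It meets a seriousness criterion, but it is not study-related. Read literally, it is not an SAE.
3. **Does 10.3 bring it back?** No. The form and the 24-hour report are required for each SAE, and step 2 has excluded the event. The wording of 10.3 shows that its author expected unrelated SAEs to exist, which is the contradiction.
4. **Does the opening of section 10 bring it back?** In part. It speaks of adverse events, so the study-related condition does not apply. But its phrase "serious and unanticipated adverse events must be reported, regardless of the cause. They" has two readings:
   - Serious events together with unanticipated events: the readmission is reported within 24 hours, to the ethics committee and sponsor only.
   - Events that are both serious and unanticipated: a serious but anticipated event is not covered at all.

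   On either reading, section 10 names neither the regulator nor the CRO and does not call for the SAE form.
5. **Does another section remove the qualifier?** No. Section 17.2, item 8, repeats the 24-hour duty for serious adverse events, and section 15 asks for their prompt reporting; neither redefines the term. Under section 11.2, monitors check that all AEs are recorded and that SAEs are reported by the standard procedure, so a site applying 10.1 literally would pass.
6. **What remains for the event?** It is an ordinary AE. Table 1 schedules AE recording at 30 days, 6 months and 12 months, and 10.2 sets no 24-hour deadline.

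The reach of the problem follows from section 14. The clinical events committee assesses death, myocardial infarction, ischemia-driven target vessel revascularization, stent thrombosis, bleeding, stroke and thrombocytopenia, with no relatedness condition. The primary endpoint (section 8.1) uses all-cause death and other events on that list. Serious events outside the list have no such second route.

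**The case against.** The strongest reply is that the sponsor's intention is plain. Two reporting rules out of three are inclusive, and reading 10.1 literally leaves 10.3 with little to do. Study-related can also be wider than drug-related, since it may take in the procedure or participation itself. An event could then be study-related but unrelated to study drug, and 10.1 and 10.3 could be partly reconciled. That much stands. It does not reconcile 10.1 with section 10, which sets cause aside altogether, and a site should not have to infer which of two conflicting texts to follow.

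It is also fair to say that these events do not vanish. They are recorded as AEs, monitors check that they are, and no endpoint in section 8 uses the SAE label. This limits the consequence and is accepted.

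Two stronger inferences are tempting, and the protocol does not support them.

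- **That the wording biases the safety comparison between arms.** The trial is open-label ("Study medications are known by both investigators and subjects"), and a reader might infer that investigators will call events unrelated more readily in one arm. But the protocol does not say who decides whether an event is study-related; section 10.2 gives investigators only the judgement of relevance to study medications. That the unblinded investigator decides is a reasonable inference, and that the decision would differ by arm is conjecture. Of the safety endpoints in section 8.3, stent thrombosis and thrombocytopenia go to the committee, which is blinded to allocation, and the third is not tied to relatedness.
- **That the loss can be counted in deaths.** Applying the death rates that section 4 cites from an earlier STEMI trial to 2,100 patients gives 2,100 × 2.1% ≈ 44 to 2,100 × 3.1% ≈ 65 deaths at 30 days, and 2,100 × 3.5% ≈ 74 to 2,100 × 4.8% ≈ 101 at one year. Those are all expected deaths, not missed ones. They come from a STEMI-only population, whereas this trial also enrols NSTEMI, and deaths are assessed by the committee whatever their cause.

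**Conclusion.** The contradiction is real and the definition in 10.1 is wrong as written. A literal reading takes serious events judged not study-related out of the SAE form and the 10.3 reporting route, and section 10 only partly covers them.

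The effect is confined to SAE classification, SAE tabulation and expedited reporting, and falls mainly on serious events outside the committee's list. The primary endpoint and the committee-adjudicated events are unaffected. No number of missed or delayed reports can be given, because the protocol offers no basis for how many serious events would be judged unrelated or how sites would read the conflict. The conclusion rests on the wording alone and on the assumption that at least some sites would apply the definition as printed.

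**What to change.** In section 10.1, replace the opening words of the SAE definition with: *Any adverse event, whether or not considered related to study treatment, that is* — followed by the existing seriousness criteria unchanged. Keep relatedness as the separate judgement already required by section 10.2. Sections 10, 10.1 and 10.3 then agree, and the term carries the same meaning in section 17.2.

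The cost is one phrase in the protocol, the matching line in any CRF instructions that repeat it, and a few more SAE forms. No endpoint, sample size or analysis changes.
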